9.2 Withdrawal or Monitoring of Participants

For the participant's protection, participants will be withdrawn immediately from the study if any of the following occur:

- 1) Cardiovascular disease (CVD) event: Typically includes MI (heart attack), PTCA (angioplasty/stenting), bypass surgery, stroke, peripheral vascular disease (arterial blockages in arms or legs leading to procedure or surgery). Less common CVD problems would be new cardiac arrhythmias (e.g., new atrial fibrillation) or new valvular disease (e.g., mitral or aortic regurgitation).
- 2) DVT/PE (deep vein thrombosis/pulmonary embolism, i.e., blood clots in the venous system).
- 3) Suicide Attempt: A participant will be withdrawn if he/she attempts suicide at any time during participation in the study.
- 4) Psychiatric Hospitalization: A participant will be withdrawn if he/she is hospitalized for psychiatric reasons at any time during participation in the study.
- 5) Pregnancy: If a participant becomes pregnant during the study she will be withdrawn from the study if using tobacco products. A pregnancy will trigger an 'Adverse Event' to be documented and this event will remain open until delivery. If the participant agrees, approximately 30 days after being withdrawn or reporting a positive pregnancy test, the research staff will call the participant to confirm her due date. The licensed medical professional will follow-up with the participant after delivery to ask questions about the baby's health and will update the open Adverse Event.
- 6) Diagnosis of severe COVID-19: If a participant reports a positive test or symptoms consistent with the diagnosis and experienced significant illness (e.g. hospitalization) they will be withdrawn from the study.

The following will be monitored and can lead to the participant being withdrawn by the PI or Licensed Medical Professional:

- 1) Blood pressure (BP) or heart rate (HR) changes: If any of the following occur post-enrollment: 1) BP is at or above 160 systolic or 100 diastolic, 2) BP is below 90 systolic or 50 diastolic **and the participant is experiencing symptoms** listed on the Blood Pressure and Heart Rate Symptom Checklist, 3) HR is at or above 105 bpm, 4) or below 45 bpm **and the participant is experiencing symptoms** listed on the Blood Pressure and Heart Rate Symptom Checklist.
- 2) Medication changes: If a participant begins taking any of the exclusionary medications or other medications that could potentially have a smoking-drug interaction post-enrollment, the medical professional will determine how best to monitor and minimize potential risks (including withdrawal if warranted). We will provide a letter to the participant that can be given to the prescribing physician and that lists potential medications that can be affected by changes in smoking that could occur as a result of participation in the study.
- 3) Any hospitalization or debilitation in which participation in the study could be detrimental to the recovery process. This will be self-reported by the participant and will be reviewed by the site PI and medical professional to determine whether continued participation in the study is appropriate.
- 4) If a participant is behaving in an inappropriate or threatening manner, admits to lying about eligibility criteria, including omitting previous medical diagnoses and medications, is participating in other smoking research studies that could affect the primary outcome measures, does not follow study instructions, etc., then the PI can withdraw him/her from the study at the PI's discretion.

- 5) If there is reason to believe the participant is sharing large quantities of the study cigarettes with other people.

Withdrawal Procedures

If the decision to withdraw a subject occurs at a study visit, regular procedures will be conducted as well as the additional early termination procedures described in 6.7. If it is determined via a phone call that withdrawal is appropriate or if the subject is dropping out, we will ask the subject to attend an exit telehealth visit to complete questionnaires, product accountability and safety assessments and to receive their final study payment.

If the subject refuses an exit visit, we will request that at the minimum, product accountability be completed. We will also stress the importance of being able to assess safety measures for the subject's safety.

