Note: The original NIH funded study design involved in person contact with the participants. This study was approved by the IRB (STUDY 00003531). Since the COVID-19 pandemic, we have limited our in-person contact while conducting human clinical trials that do not have a direct therapeutic benefit to the participant. Because it is unknown when we will be able to conduct the originally designed trial again and the uncertainty regarding the course of the pandemic, we have adapted this original study to be conducted primarily remotely, with a brief clinic or curbside component to drop off biosamples and pick up study cigarettes. The recent improvements in controlling the COVID-19 virus

has allowed us to conduct some of our measures face-to-face. As the situation continues to improve, we propose to resume the inhalation measures on a subset of study participants.

3 Summary

The **primary aim** of this study is to examine the effects of unventilated vs. ventilated filter cigarettes on an exposure biomarker of a potent lung carcinogen and smoking behaviors (e.g., cigarettes per day, filter analysis).

A **secondary aim** includes determining the effects of unventilated vs. ventilated filter cigarettes on cigarette dependence and subjective response to cigarettes.

Study Design

This is a randomized, single-blind, multi-site study where subjects (N=162; 81 in each group) are randomly assigned to one of two cigarettes with different filter designs: 1) Ventilated cigarettes; or 2) Unventilated cigarettes.

4 Subject Selection

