5.10 Early Termination

Procedures for Early Termination Telehealth Visits

If a subject decides to withdraw from the study prior to completion or if they are withdrawn by the Project Leader due to safety concerns, they will be scheduled for an early termination visit. If the participant is contacted within the window of a regularly scheduled visit, all measures for that visit will be collected. If the early termination visit occurs at Weeks 1, 2, 4 or 5, additional safety measures will be obtained since these measures are not scheduled at those visits. If the subject is seen outside the regularly scheduled visit window, safety measures will be obtained.

A. Physiological Measures:

- 1) Vital signs (blood pressure & heart rate) will be obtained while conducting the telehealth visit.
- 2) Carbon monoxide level will be obtained while conducting the telehealth visit.
- 3) Biomarker collection (first void or spot urine and saliva) collected prior to or at the telehealth visit and then dropped off at the brief clinic or curbside visit.

B. Surveys – *link sent to participant to complete REDCap based survey:*

The following additional assessments will be completed at early termination via REDCap, if not part of the usual measures scheduled for the regularly scheduled visit:

Subjective Outcome Measures:

- 1) Respiratory Symptoms and Global Health Questionnaire
- 2) Perceived Health Risk
- 3) Modified Cigarette Evaluation Scale – Study cigarette
- 4) Cigarette Purchase Task – Study Cigarette
- 5) Nicotine Dependence Questionnaire
- 6) Duke Sensory Questionnaire - Study Cigarette
- 7) Tobacco Policy Support Questionnaire
- 8) End of Study and Feasibility Questionnaire

C. Interviews - Research Assistant interviews participant and enters directly into REDCap:

- 1) COVID-19 Assessment
- 2) Health Changes and Menstrual Cycle Questionnaire
- 3) Adverse Event
- 4) Concomitant Medications
- 5) Daily ITR Review (follow-up on missing and unusual reports)
- 6) Timeline Follow-back Questionnaire
- 7) Intention to Quit
- 8) Product Accountability Log
- 9) Smoking Cessation Counseling
- 10) End of Visit Evaluation

5.11 Study Completion:

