To determine the sample size for a test of non-inferiority for unventilated filter cigarettes compared to ventilated filter cigarettes (control group), we used pilot data from our original ventilated/unventilated study 1 ([name], personal communication). For the purposes of sample size considerations, we will focus on total NNAL as one of the primary outcomes. Seventy subjects had a baseline NNAL value while smoking their usual brand and 19 and 16 subjects had an end of study NNAL value for the ventilated and unventilated groups, respectively. The endpoint of interest is the change in NNAL from baseline. To normalize the distribution of NNAL, the calculations were performed in the log scale. The non-inferiority margin (NIM) was set at a 15% change between groups. This criterion was chosen because it is close to, but not greater than the upper limit of the 95% confidence interval (CI) for the geometric mean of the change in NNAL. Therefore, 73 subjects per group will achieve 80% power to detect non-inferiority for the mean change in NNAL using a one-sided, two sample t-test with a significance level of 0.05. Furthermore, with these sample sizes, a one-sided, two-sample t-test for the mean difference in cigarettes per day (CPD) from baseline will have 90% power to determine non-inferiority with a significance level of 0.05 if the NIM is 2 cigarettes. A mean difference between ventilation groups of less than 2 cigarettes is considered to be in the range of equivalence. To accommodate a 10% loss-to-follow-up rate, we plan to enroll 81 subjects per group for a total of 162.

Study Populations

Intent-to-treat

The first analysis of all primary and secondary endpoints will adhere to the intent-to-treat principle. Under this principle, all subjects randomized to one of the two study arms will be included in the analysis in the group to which they were randomized regardless of protocol violations and compliance to treatment assignment.

Per-Protocol

A second per-protocol analysis will include only participants who complete the 6 week visit without protocol violations or non-compliance.

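### Discretionary withdrawal for non-compliance (section 9.2) sits in tension with the intent-to-treat analysis (section 10.1), because outcome collection is not kept going to Week 6

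*Combined protocol and SAP*

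**What the plan says.** **Withdrawal.** Section 9.2 lists grounds that are monitored and may lead to removal. Item 4 covers threatening conduct, untruthfulness about eligibility, joining another smoking study, and a participant who "does not follow study instructions, etc., then the PI can withdraw him/her from the study", as a matter of discretion. Removal is from the study, not only from the study cigarettes, and may come before or after randomisation.

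**What happens next.** Under the withdrawal procedures in 9.2, a decision taken at a visit leads to that visit's usual procedures plus the early termination procedures (cross-referenced to a section 6.7; they stand in 5.10). If the decision is taken by phone, the participant is asked to "attend an exit telehealth visit to complete questionnaires, product accountability and safety assessments and to receive their final study payment". That list names no biological sample. Section 5.10 schedules early termination for participants who choose to leave or are "withdrawn by the Project Leader due to safety concerns, they will be scheduled for an early termination visit". Removal for non-compliance is not named there. The 5.10 procedures include "Biomarker collection (first void or spot urine and saliva) collected prior to or at the telehealth visit", and the procedure table marks total NNAL at early termination. If contact falls within a scheduled visit window, all of that visit's measures are taken.

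**Analysis.** Section 10.1 places every randomised subject "in the group to which they were randomized regardless of protocol violations and compliance to treatment assignment". It adds: "A second per-protocol analysis will include only participants who complete the 6 week visit without protocol violations or non-compliance". Section 10.2 ties both primary endpoints to Week 6: NNAL at that visit, and mean CPD over the 7 days before it. The primary analysis is a one-sided two-sample t-test for non-inferiority.

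**Blinding.** The Study Design paragraph of section 3 states: "This is a randomized, single-blind, multi-site study". At visit 00 (section 5.6), reading the script for the assigned arm is listed among the research assistant's tasks.

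**The concern.** Non-compliance can end a participant's observation under one section and is irrelevant to inclusion under the other. No text keeps a person withdrawn for non-compliance under observation until Week 6. Inclusion in the intent-to-treat set is then nominal for that person: the arm is known and the outcome is not.

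Two things could follow. First, the primary comparison could drift towards the compliant remainder of each arm, through decisions that depend on behaviour after randomisation and may be taken with knowledge of the arm. Section 5.12 itself expects taste and withdrawal symptoms to be sources of difficulty, so non-compliance may relate to the assigned cigarette. Second, avoidable loss may be added to the 10% allowed for in the sample size.

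**Working it through.** **1. What is observed after a non-compliance withdrawal**

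| When and how decided | Week 6 NNAL | CPD, 7 days before Week 6 | Other data |
|---|---|---|---|
| At a visit before the Week 6 window | No | No | Urine and saliva on exit; daily texts to that point |
| By phone before the Week 6 window | No | No | Questionnaires, accountability, safety; no biosample named |
| Within the Week 6 window | Yes (5.10: all measures of that visit) | Yes, if texts are complete | - |

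No rule says that an exit NNAL value stands in for Week 6. The gap is therefore confined to withdrawals before the Week 6 window.

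**2. What the plan offers for a missing Week 6 value (10.2)**

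- Primary t-test: needs the Week 6 value.
- Mixed model over all visits from visit 00: can use Week 3 NNAL and earlier CPD, but is a secondary analysis.
- Multiple imputation: described as a sensitivity analysis, with regression models built from baseline covariates. These do not carry the later behaviour that led to removal.

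**3. The plan's own sample size**

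Inputs from 10.1: 73 per group; 80% power for NNAL at a 15% margin; 90% power for CPD at a margin of 2 cigarettes; one-sided 0.05; 10% loss; 81 enrolled per group. 73 / 0.9 = 81.1, and 81 × 0.9 = 72.9, so the stated 81 is reproduced to within rounding.

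No SD is stated. I solved for it from the stated power with the noncentral t distribution, taking the true difference as 0 and n = 73 per arm:

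- log NNAL change: margin ln(1.15) = 0.1398, power 0.80, giving SD = 0.338
- CPD change: margin 2, power 0.90, giving SD = 4.11

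**4. Power if withdrawals come on top of the 10% (assumption)**

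| Extra loss | n per arm | NNAL power | CPD power |
|---|---|---|---|
| 0% | 73 | 80% | 90% |
| 5% | 81 × 0.85 = 68.9, say 69 | 78% | 88% |
| 10% | 81 × 0.80 = 64.8, say 65 | 76% | 87% |
| 15% | 81 × 0.75 = 60.8, say 61 | 73% | 85% |

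**5. Bias illustration (assumption throughout)**

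A share f of the unventilated arm is withdrawn and nobody in the ventilated arm. Their log NNAL change would have been d higher than in those retained. The true all-randomised difference equals the margin. The difference among those retained is then too small by f × d. The standard error is 0.338 × √(2/73) = 0.0559, holding n at 73 per arm. The chance of declaring non-inferiority is approximately Φ(f × d / 0.0559 − 1.645); the table uses the noncentral t.

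| f | d | f × d | False non-inferiority (nominal 5%) |
|---|---|---|---|
| 5% | 0.15 | 0.0075 | 6.5% |
| 5% | 0.30 | 0.015 | 8.4% |
| 5% | 0.50 | 0.025 | 11.5% |
| 10% | 0.15 | 0.015 | 8.4% |
| 10% | 0.30 | 0.030 | 13.3% |
| 10% | 0.50 | 0.050 | 22.5% |

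With the sign of d reversed at f = 5%, the rate falls to 3.8% (d = −0.15) or 1.8% (d = −0.50), so the test becomes conservative. If the same share is withdrawn in both arms with the same excess, the two shifts cancel and there is no bias.

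**The case against.** A conduct rule and an analysis-set definition do different jobs, and many trials have both. A withdrawn participant remains in the intent-to-treat set with a missing value. That stands: the passages are in tension, not in strict contradiction.

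A reader might go further and infer that the intent-to-treat analysis becomes impossible, or that withdrawn participants leave no outcome data. The documents support neither. Exit urine with NNAL is provided for, visit-window measures are complete, the mixed model uses earlier visits, and imputation is planned, separately by arm if missingness is associated with arm.

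The protocol also meets most non-compliance with counselling and honest reporting (5.12, 5.15). Abstainers keep to the visit schedule (5.13). The per-protocol definition excludes non-compliers as well as non-completers, which presupposes that some non-compliers are retained. Screening requires 5 days of text compliance, and about three weeks of baseline phases precede randomisation. Discretionary withdrawals may therefore be few.

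A reader might also infer that withdrawals will be made with the arm in mind. Single-blinding permits this, but no text says that the PI who decides knows the assignment; the script is listed among the research assistant's tasks.

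Finally, off-product participants can dilute a non-inferiority contrast, so retaining them has a cost. That is true, but the per-protocol set already addresses it. If their Week 6 data are collected, both analyses can be run on observed values.

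**Conclusion.** The point holds as a gap in outcome follow-up and a cheap improvement to the plan. After discretionary withdrawal for non-compliance before the Week 6 window, nothing provides for a Week 6 NNAL or the final 7 days of CPD, and the primary t-test cannot include that person. The mitigations are partial: exit samples have no assigned role in the primary analysis, the mixed model is secondary, and imputation is labelled a sensitivity analysis on baseline covariates.

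The size is unknown, because no withdrawal rate is given and nothing says whether the 10% allowance already covers these withdrawals. The power cost is modest: about 2 points for each outcome if a further 5% are lost. The potential for bias matters more, but the 6.5-11.5% range (5% withdrawn) and the 8-22% range (10% withdrawn) rest wholly on one-arm withdrawal with higher NNAL among those removed. They show sensitivity and do not predict what will happen. Reading them as evidence that the trial favours non-inferiority would go beyond the documents.

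**What to change.** Reconcile section 9.2 item 4 with the intent-to-treat text in 10.1 by separating removal for non-compliance from the end of outcome collection:

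- After randomisation, where non-compliance is the only issue and the participant still consents, continue to seek the Week 6 urine and the daily texts for the 7 days before Week 6 on the original schedule.
- Analyse these participants as randomised for intent-to-treat and exclude them only from the per-protocol set.
- Record the reason for every PI-discretion withdrawal and tabulate reasons by arm.

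Safety withdrawals, removal for threatening behaviour, and whether study cigarettes continue to be supplied are for the sponsor and are not questioned here.

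The cost is about one protocol sentence, one table, and the visit and sample payments for the participants retained. Some will not cooperate. Those who do may dilute the intent-to-treat contrast somewhat, which the per-protocol analysis will show.

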9.3 Management of SAEs and Other Study Risks

Subjects will be screened for any potentially compromising medical condition and will be monitored throughout the study. Subjects who experience any adverse side effects of concern will be reviewed by the study's licensed medical professionals, sent to the emergency clinic or referred to their physician, depending on the nature and severity of the adverse event.

Subjects will be encouraged to quit smoking and optimally all tobacco use at the end of study and we will conduct a 4 week follow-up to assess tobacco use status. If necessary, we will continue follow-up to make sure that no greater harm is experienced by the subject and to continue to encourage quit attempts. If biomarker analysis determined significantly greater exposure to toxicants than prior to the study, the subject will be contacted to discuss the results and cessation of all tobacco products will be strongly recommended.

The site medical professional will review all AEs. A study participant may be discontinued from the study if the medical professional and/or PI determine it is the best decision in order to protect the safety of a participant. In the event that a participant either withdraws from the study or the investigator decides to discontinue a participant due to an AE/SAE, the participant will have appropriate follow-up medical monitoring. The participant experiencing an AE/SAE will be followed until the problem resolves, stabilizes, or is clearly unrelated to the study cigarettes. Any AE that remains open will be reviewed and closed at the 30 day follow-up interview.

9.4 Reporting of SAEs to the IRB, FDA, and NCI

Serious or unexpected adverse events (SAE or SUSAR) as defined in 21 CFR 312.32 (death, life-threatening, hospitalization (initial or prolonged), disability or permanent damage, congenital anomaly/birth defect, required intervention to prevent permanent impairment or damage (devices), other serious events (important medical outcomes) that are related or possibly related to study participation will be reported to the Administrative Core, all site IRBs (annually unless a Reportable Event), the NCI Project Officer, FDA, and the Data Safety and Monitoring Board. Site IRBs require that fatalities related to the study be reported promptly.

Reports of all unexpected product related SAEs will also be documented within FDA's SAE data monitoring system, within 72 hours

Reporting of IRB Actions to NCI

Actions taken by the local IRBs in response to SAEs will be reported to NCI in the annual noncompetitive continuation application, as will reports of changes or amendments to the protocol as a result of an SAE. Recommendation for trial discontinuation, significant changes or amendments to the protocol, or other significant findings as a result of an SAE will be reported immediately to the NCI Project Officer by the Project PI.

Reporting Changes or Amendments to the Protocol

Any changes or amendments to the protocol made in response to adverse events/SAEs will be reviewed by PIs and then requested in writing to the IRB, which will then grant or deny permission to make the requested change in protocol. The DSMB, FDA and NCI will be notified about any significant changes to the protocol. NCI will be informed of any approved changes in protocol by documentation in the noncompetitive continuation application. Changes that significantly alter the scope of the research or the ability of the research to achieve its specific aims will be submitted to the DSMB, FDA, and NCI for approval prior to implementation.

10 Statistical Considerations

10.1 Trial Endpoints

Primary Endpoint:

- The change in total NNAL from visit 00 to week 6 visit.
- The mean CPD based on 7-day IVR data between week 00 and Week 6 visit

Secondary Endpoint:

- Change in TNE, CEMA, and PheT from visit 00 to week 6 visit
- Change in intensity of smoking measured by filter analysis collected at 00, Week 3 and Week 6.
- Change in parameters of inhalation depth measured at 00 and Week 6.
- Change in subjective measures (dependence as measured by the FTND, mCES, and Perceived Health Risk) from visit 00 to Week 6 visit.

Exploratory Endpoints:

- Change in biomarkers of other volatile organic compounds (e.g.,3-HPMA, HMPMA) from visit 00 to Week 6 visit.
- Determine concordance in biomarkers of exposure across different sample collection methods.

Secondary Endpoint

Safety Endpoints:

- Adverse Events (AEs)

- Serious adverse events (SAEs)

Randomization

Subjects will be randomly assigned using a stratified (by site), block randomization scheme into the following groups: (1) ventilated filter cigarettes; or (2) unventilated filter cigarettes.

Sample size and power considerations

To determine the sample size for a test of non-inferiority for unventilated filter cigarettes compared to ventilated filter cigarettes (control group), we used pilot data from our original ventilated/unventilated study 1 ([name], personal communication). For the purposes of sample size considerations, we will focus on total NNAL as one of the primary outcomes. Seventy subjects had a baseline NNAL value while smoking their usual brand and 19 and 16 subjects had an end of study NNAL value for the ventilated and unventilated groups, respectively. The endpoint of interest is the change in NNAL from baseline. To normalize the distribution of NNAL, the calculations were performed in the log scale. The non-inferiority margin (NIM) was set at a 15% change between groups. This criterion was chosen because it is close to, but not greater than the upper limit of the 95% confidence interval (CI) for the geometric mean of the change in NNAL. Therefore, 73 subjects per group will achieve 80% power to detect non-inferiority for the mean change in NNAL using a one-sided, two sample t-test with a significance level of 0.05. Furthermore, with these sample sizes, a one-sided, two-sample t-test for the mean difference in cigarettes per day (CPD) from baseline will have 90% power to determine non-inferiority with a significance level of 0.05 if the NIM is 2 cigarettes. A mean difference between ventilation groups of less than 2 cigarettes is considered to be in the range of equivalence. To accommodate a 10% loss-to-follow-up rate, we plan to enroll 81 subjects per group for a total of 162.

Study Populations

Intent-to-treat

The first analysis of all primary and secondary endpoints will adhere to the intent-to-treat principle. Under this principle, all subjects randomized to one of the two study arms will be included in the analysis in the group to which they were randomized regardless of protocol violations and compliance to treatment assignment.

Per-Protocol

A second per-protocol analysis will include only participants who complete the 6 week visit without protocol violations or non-compliance.

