10.2 Statistical analysis plan

The primary objective of the statistical analysis is to compare the effects of cigarette ventilation between two study groups: ventilated filter cigarettes and unventilated filter cigarettes. All statistical analyses will be performed using SAS version 9.4 (SAS Institute Inc., Cary NC) and a p-value less than 0.05 will be considered significant.

Describing the Study Population

Descriptive statistics will be performed for data collected on demographic characteristics, subjective measures and biomarkers at different phases and visits. Baseline data will be compared between the two ventilation groups with the two-sample t-test or the non-parametric Wilcoxon rank sum test for continuous or ordinal variables and chi-square tests for categorical variables. Biomarker data may be log transformed if necessary.

Primary Endpoint Analysis

The primary endpoints are (1) the total NNAL at the 6-week visit adjusted for NNAL at end of Phase 2 (visit 00); and (2) the mean CPD based on 7 days ITR data before week 6 visit adjusted for the mean CPD during Phase 2 (visit 00). The analysis of these two endpoints will evaluate non-inferiority of the unventilated group compared to the ventilated group.

Primary Analysis

The primary analysis will be a one-sided, two-sample t-test for non-inferiority. The null hypothesis for total NNAL (analyzed in the log scale) is that the increase from end of Phase 2 (visit 00) is 15% greater in the unventilated group compared to the ventilated group. The NNAL alternative hypothesis is that the increase from baseline (visit 00) is no higher than 15% in unventilated over ventilated groups. If the null hypothesis is rejected in favor of the alternative hypothesis, we will conclude that the unventilated filters are no more harmful in terms of NNAL exposure than the ventilated filter and may actually be less harmful. Similarly for the CPD, the non-inferiority t-test will have a null hypothesis that the 6 week mean increase in CPD from end of Phase 2 (visit 00) for the unventilated group is greater than 2.0 cigarettes compared to the ventilated group. The alternative hypothesis is that the CPD increase in the unventilated group is no more than a mean of 2.0 cigarettes verses the CPD increase in the ventilated group and the unventilated group may even smoke fewer cigarettes.

Secondary Analysis

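### The conclusion planned for the NNAL test drops the 15% margin: rejecting the null rules out a rise of 15% or more, not any rise.

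*Combined protocol and SAP*

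**What the plan says.** Section 10.1 (Sample size and power considerations) frames NNAL as a non-inferiority comparison of unventilated with ventilated cigarettes: "The non-inferiority margin (NIM) was set at a 15% change between groups". The reason given, referring to NNAL change, is that "it is close to, but not greater than the upper limit of the 95% confidence interval (CI) for the geometric mean". The data described there come from a pilot in which "19 and 16 subjects had an end of study NNAL value for the ventilated and unventilated groups, respectively". No SD, interval limits or point estimate are given.

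Section 10.2 (Primary Analysis) says "The primary analysis will be a one-sided, two-sample t-test for non-inferiority". The NNAL null places the unventilated excess at 15%, and the alternative is that the excess is no higher than 15%. The next sentence gives the conclusion to be drawn on rejection: "we will conclude that the unventilated filters are no more harmful in terms of NNAL exposure than the ventilated filter". It goes on to say that unventilated filters might in fact be less harmful. No superiority test and no confidence-interval condition is attached to either statement.

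**The concern.** The margin is present in both hypotheses and absent from the conclusion. A reader of the result would be told that NNAL exposure is not higher, when the data need only show that it is not higher by 15% or more.

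This matters more here than in many non-inferiority trials. Section 2 gives the overarching goal as making sure that a ban on filter ventilation would not raise toxicant exposure. Section 6.2 chooses NNAL to represent exposure to carcinogenic tobacco-specific nitrosamines. Section 8 expects the results to help the regulator decide how to act. On that question, none higher and less than 15% higher are different answers.

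The shorter wording could be defended if the plan had argued that a rise below 15% is of no consequence. For cigarettes per day, section 10.1 at least describes a difference under 2 cigarettes as within a range of equivalence. For NNAL it makes no such statement.

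**Working it through.** **Logic.** Let R be the true ratio, unventilated to ventilated, of the geometric mean change in NNAL. The null is R at or above 1.15 and the alternative is R below 1.15. Rejecting at one-sided 0.05 is the same as finding the upper limit of the two-sided 90% CI below 1.15. That is compatible with R below, equal to or moderately above 1. A claim that R is not above 1, or is below 1, needs information that this rejection does not carry.

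**Inputs from section 10.1.** "73 subjects per group will achieve 80% power to detect non-inferiority for the mean change in NNAL"; "one-sided, two sample t-test with a significance level of 0.05"; the 15% margin; and "the calculations were performed in the log scale".

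**Assumptions, because the plan is silent.** The 15% is read as a ratio of 1.15, so the margin is ln(1.15) = 0.1398. The true ratio used for planning is taken as 1.0, in line with the hypothesis in section 1.2. The SD of the log change is not stated.

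**The plan's own figure.** Without an SD, 73 per group cannot be reproduced independently. It can only be solved backwards:

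- Normal approximation: SD = 0.1398 × √(73/2) / (1.645 + 0.842) = 0.340.
- Noncentral t: SD = 0.338.

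Putting either value back returns 73 by construction, so this does not confirm the sample size.

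**Largest observed ratio that still passes, at SD 0.338 and 73 per group.**

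- SE = 0.338 × √(2/73) = 0.0559.
- Largest passing log ratio = 0.1398 − 1.656 × 0.0559 = 0.0471, a ratio of 1.048.
- Two-sided 95% CI at that point = exp(0.0471 ± 1.96 × 0.0559) = 0.94 to 1.17.

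So, under these assumptions, an observed rise of up to about 4.8% would be reported as not more harmful.

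**Sensitivity to the unstated SD (73 per group, same formula).**

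| SD of log change | Largest passing observed ratio |
|---|---|
| 0.20 | 1.089 |
| 0.30 | 1.059 |
| 0.338 (back-solved) | 1.048 |
| 0.40 | 1.031 |
| 0.50 | 1.003 |
| 0.60 | 0.976 |

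With 81 per group and SD 0.338 the limit is 1.053. Reading the 15% as 0.15 on the log scale, or as −ln(0.85), and solving the SD again gives 1.052 and 1.056 at 73 per group.

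**The case against.** The strongest defence is that this is ordinary non-inferiority shorthand. The 15% stands in the two sentences just before the conclusion, so a careful reader has it to hand. The test itself is valid. Both points are fair, and they make this a fault of wording. They do not remove it: the sentence is the pre-specified conclusion, it can be quoted without the hypotheses, and its second half, about possibly less harm, goes beyond the shorthand.

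Four stronger readings are tempting, and the documents do not support them.

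- *The margin merely measures the pilot's imprecision, and a noisier pilot would have loosened it.* Section 10.1 does not say whether the interval is between groups, within an arm or pooled, and gives neither limits nor an estimate. It says only that 15% does not exceed the upper limit. What can be said is that no other rationale is offered.
- *A statistically significant increase would be reported as not more harmful.* At 73 per group this needs an SD below about 0.23. An SD of 0.20 has no source in the plan. If it were to come from baseline adjustment, which with equal variances at visit 00 and week 6 multiplies the change-score SD by √((1+r)/2), then (0.20/0.338)² = 0.35 and r = 2 × 0.35 − 1 = −0.30. A negative correlation between repeat NNAL values in the same smoker is implausible. The regression with baseline is also placed under Secondary Analysis, whereas the conclusion is tied to the t-test.
- *The test errs too often.* At SD 0.338 it would reject in 49% of trials if the true ratio were 1.05 and in 20% if it were 1.10. Both ratios lie inside the margin, so rejection is correct there. Only the words attached to it are wrong.
- *A finding of not higher should require an upper bound at or below 1.* That is a superiority criterion. With truly equal exposure, a one-sided 95% bound would meet it about 5% of the time. Whether to impose it is debatable, and the correction does not depend on it.

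**Conclusion.** The point holds as a mismatch between test and conclusion. It follows from section 10.2 alone and needs no assumed figure: a rejection that excludes a 15% excess is to be reported as no excess and possibly a reduction, and section 10.1 offers no exposure- or health-based argument that would close the gap.

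The size is illustrative. The figure of about 1.048 rests on an SD solved back from the plan's sample size, power and margin with a true ratio of 1.0. It should be shown with its range, 1.089 to 1.003 for SDs of 0.20 to 0.50. At an SD of 0.60 the observed ratio would itself have to be below 1 to pass, so the practical gap shrinks as variability grows.

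A reader might infer that the non-inferiority test is flawed or that 15% is the wrong margin. The documents establish neither.

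**What to change.** Keep the test, the margin and the sample size. In section 10.2:

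1. Replace the conclusion on rejection with: *we will conclude that an increase in NNAL of 15% or more relative to ventilated cigarettes has been excluded.*
2. Report the geometric mean ratio with its 90% CI, which matches the one-sided 0.05 test, and its 95% CI.
3. Drop the statement about possibly less harm unless the confidence interval supports it.
4. State the basis of the 15% margin beside the result, including what kind of interval it was taken from.

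This is a change of SAP wording and reporting, with no effect on conduct. The downside is a more modest claim.
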